#### 3.3.3 Safety population

The safety population will consist of all randomised participants. Participants will be grouped according to treatment received.

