#### 5.2.6 Main study (Phase 2)

Progression criteria from Phase 1 to Phase 2:

- all centres participating in the pilot are recruiting (in one or more specialties);
- at least 40% of eligible patients are consenting to randomisation;
- each centre recruiting >8 patients/month (from any specialty);
- interventions are delivered according to the protocol in all centres;
- the allocated intervention is initiated in >=90% of randomised participants;
- >=70% of patients randomised to high resistance IMT or low IMT adhere to allocated interventions (adherence will be recorded electronically by the IMT device); we will define a patient as adherent with the intervention if they use the IMT device at least five days a week (for a minimum of 30 breaths per day).

If progression criteria are met, recruitment will continue at the Phase 1 hospitals and we will begin recruitment at a minimum of an additional two hospitals (depending on how recruitment is going in Phase 1). Delivery mode of the intervention will be based on the findings in Phase 1 and any amendments to the study will be submitted for approval by the regulatory authorities.

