#### 5.6.7 Usual care protocol

Participants will be given advice about the importance of deep breathing exercises and provided with a leaflet containing written information on peri-operative deep breathing exercises. The usual care leaflet will also be given to participants in the IMT groups.

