#### Overview

Serious and other adverse events (AEs) will be recorded and reported in accordance with GCP guidelines and BTC (CTEU)'s Serious Adverse Events and Safety Reporting Standard Operating Procedure (SOP-GE-012) (see Figure 2).

[figure not shown]
INSPIRE Protocol Version 2.0 As there are no known long term safety concerns associated with using IMT, and any adverse events associated with IMT can only occur whilst the participant is undertaking IMT, safety reporting to the Sponsor will take place only while the participant is exposed to the intervention. In practice this means that the SAE reporting period will commence at the training session and continue until the patient is admitted to hospital for their index procedure. SAEs may be identified by ad hoc reporting from the patient, data collection at the extra training visits (where applicable) or on admission to hospital.

The complications or side effects of IMT, i.e. 'expected events' may include: dyspnoea, headache, pain, cough, nausea, chest discomfort, tachycardia, bradycardia, syncope, hypertension, bronchospasm, dizziness, syncope, epistaxis, respiratory distress, respiratory failure, perforated eardrum, cephalalgia. Any other event will be considered 'unexpected'. It is worth noting that the 'expected events' are events considered in other RCTs of IMT, but none of the RCTs have reported differences in the rate of any of these events between IMT/non-IMT groups, therefore these events may be regarded as hypothetical.

All unexpected and fatal SAEs will be reported to the coordinating centre, who will check the report and then forward to the Sponsor. Reporting to the Sponsor will occur within 24 hours of the site team becoming aware of the event. If the event is ongoing at the time of initial reporting the participant will be actively followed up and a follow-up report will be provided within 5 days of the initial report. Further follow up reports will be submitted only when there has been a significant change/update of the SAE until the SAE has resolved, or a decision for no further follow-up has been taken by the local PI.

All AEs during the participant's hospital stay and SAEs after hospital discharge will be recorded in detail on a CRF. At the conclusion of the study, all AEs recorded during the study will be subject to statistical analysis, and the analysis and subsequent conclusions will be included in the final study report.

Figure 2 Serious adverse event reporting flow chart

9.3

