#### 3.3 Analysis populations

#### 3.3.1 Intention-to-treat population

Analyses and summaries will be performed on an intention-to-treat basis. Analyses will use data from all participants randomised. The ITT population will consist of all randomised participants, included according to their randomised allocation, regardless of whether they are ineligible, prematurely discontinue treatment or are otherwise protocol deviators.

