#### 4.5.4 Harms

Adverse events will be summarised by MedDRA system organ class. Furthermore, adverse events and serious adverse events collected throughout the trial will be tabulated.

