**Table A8: Protocol deviations** 

	Cai	rdiac	Non-c	ardiac	Ove	erall
	n	%	n	%	n	%
Non-adherence to the intervention						
Intervention not delivered per protocol						
Less than 2 weeks IMT training						
More than 8 weeks IMT training						
Missed all training						
More training than recommended (>2x 15min sessions/d)						
Continue training after surgery						
Not training at the recommended intensity (high resistance IMT group only)						
Other monitoring of study intervention						
Undergone surgery prior to completing the intervention						
Surgery delayed because of intervention						
Other non-compliance						
Ineligible but randomised						
Did not receive allocated intervention (cross- over)						

Table to be repeated with participants grouped by randomised allocation

Table A9: Details on randomisation and intervention timings

	Car	diac	Non-c	ardiac	Overall		
	n	%	n	%	n	%	
Days between randomisation and surgery (Median, IQR)							

Table to be repeated with participants grouped by randomised allocation

Section 3: Primary and secondary outcomes

Table A10: SWAT primary and secondary outcomes

		Automatic load + Additional visit (n=XX)	Manual load + Additional visit (n=XX)	Automatic load + No additional visit (n=XX)	Manual load + No additional visit (n=XX)
PRIMARY OUTC	OME				
Training load	Baseline				
	Day of surgery*				
	Change from baseline				
SECONDARY OL	ITCOMES				
Work	Baseline				
	Day of surgery*				
	Change from baseline				
MIP	Baseline				
	Day of surgery				
	Change from baseline				
FEV 1	Baseline				
	Day of surgery				
	Change from baseline				
FVC	Baseline				
	Day of surgery				
	Change from baseline				

Inspire SAP, version v0.3 05/07/2024
In accordance with v3.0 of the study protocol

Proportion of participants following at least 80% of the planned training sessions

Recorded on patient diary

Recorded on KHP2 device

Proportion of participants training at the prescribed intensity score of (RPE rating )

First, second and last line of patients diary

Most recent 10 sessions at additional visit

(participants randomised to additional visit only)

Table A11: Primary and secondary outcomes

Outcome	Randomised to IMT (n=xx)	Randomised to Sham IMT/Usual care (n=xx)	Randomised to Sham IMT (n=xx)	Randomised to usual care (n=xx)	Effect (95% CI)*	p-value
Any PPC					RD/RR	
Respiratory infection					-	-
Respiratory failure					-	-
Pleural effusion					-	-
Atelectasis					-	-
Pneumothorax					-	-
Bronchospasm						

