Skin / Subcutaneous tissue												
Musculoskeletal / Connective tissue / bone												
General												
Anatomical / Surgical dam												
Oncology												
Investigations												
Injury												

	Randon AEs	nised Pa	ntients (N=XXX SAEs	•		R	Intensity (SAEs) Unanticipated events only					
	Events/ Patients	% 	Events/ Patients	% 	Not related	Unlikely to be related	Possibly related	Probably related	Definitely related	Mild	Moderate	Severe
Re-operation												
Chemo / Radio												
Any event not anticipated												
		•							_			·

Table of events (excluding relatedness and intensity) to be repeated with participants grouped by treatment received

Table A14: Adverse events reported at 3 and 6 month follow-up

	Randomise (n=2	ed patients XX)			Relatedness			Intensity (Unanticipated events only)			
	Event Patients	% 	Not related	Unlikely to be related	Possibly related	Probably related	Definitely related	Mild	Moderate	Severe	
Any anticipated event											
Infective											
Cardiovascular											
GI											
Respiratory/pulmonary											
Nervous system / Neurological / Psychiatric											
Immune system											
Metabolism / Nutrition											
Eye											
Ear / Labyrinth											
Hepatobiliary											

	Randomise (n=2	ed patients XX)			Relatedness			Intensity (	Unanticipated e	events only)
	Event Patients	% 	Not related	Unlikely to be related	Possibly related	Probably related	Definitely related	Mild	Moderate	Severe
Renal / Urinary										
Reproductive / Breast										
Skin / Subcutaneous tissue										
Musculoskeletal / Connective tissue / bone										
General										
Anatomical / Surgical dam										
Oncology										
Investigations										
Injury										
Re-operation										
Chemo / Radiotherapy										
Any event not anticipated										

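### The only by-arm split of adverse events uses an undefined treatment received, although the events tabulated arise after training has ended; a by-allocation version should be added.

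*SAP*

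**What the plan says.** SAP 3.3.3 defines the population and the grouping together: "The safety population will consist of all randomised participants. Participants will be grouped according to treatment received". SAP 3.3.1 gives the general rule: "Analyses and summaries will be performed on an intention-to-treat basis". SAP 4.5.4 (Harms) adds no grouping rule and says only that "adverse events and serious adverse events collected throughout the trial will be tabulated".

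In Appendix A, the main columns of Tables A13 (index admission) and A14 (3 and 6 months) pool all randomised patients. (Table numbers here follow the captions; the list of outputs at the start of the appendix numbers them differently.) The by-arm version comes from a footnote to each: "Table of events (excluding relatedness and intensity) to be repeated with participants grouped by treatment received". No by-arm version of Table A15 (serious events throughout the trial) is mentioned. Table A11, which holds any postoperative pulmonary complication (PPC), the PPC components, ventilation and mortality, is headed by randomised group.

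Three protocol statements bear on what treatment received could mean:

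- Usual care is advice plus a leaflet, and Protocol 5.6.7 says "The usual care leaflet will also be given to participants in the IMT groups".
- One progression criterion in Protocol 5.2.6 is that "the allocated intervention is initiated in >=90% of randomised participants".
- Under Safety reporting (Overview), "All AEs during the participant's hospital stay and SAEs after hospital discharge will be recorded in detail on a CRF". This collection does not depend on whether IMT was started. The same section says that harms from IMT can arise only while a participant is doing it.

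**The concern.** Grouping by exposure is a usual choice for harms when the events could be caused by the exposure. Here the protocol itself limits possible IMT harms to the training period. The two tables that get the treatment-received split cover the time from admission onward, when surgery and the patient's condition drive most events. In that period a by-allocation table would be a randomised comparison, and the plan does not provide one.

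The missing definition adds to this. With no minimum exposure and no category for people who received nothing, the handling of non-starters would be settled at analysis. Because all three arms get the leaflet, a device-arm participant who never used the device could be said to have received usual care. Movement the other way would be rare: the usual care arm has no trial device, and Protocol 5.6.4.1 regards participants obtaining their own as unlikely.

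At stake is the by-arm comparison of all adverse events that Table A11 does not carry. Safety is a stated aim of the trial, and the protocol commits to a statistical analysis of adverse events with conclusions in the final report.

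**Working it through.** **Step 1: which period each table covers**

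| Output | Period | By-arm grouping |
|---|---|---|
| Table A11: PPC, components, ventilation, mortality | after surgery | randomised allocation |
| Table A13: adverse and serious adverse events | index admission | treatment received |
| Table A14: adverse events | 3 and 6 months | treatment received |
| Table A15: serious adverse events | whole trial | none mentioned |

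The exposure-based split is therefore requested for the two periods after training, and no by-arm table is dedicated to the training window. Table A13 has rows for pneumonia and respiratory infection. These could be grouped differently from the respiratory rows of Table A11.

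**Step 2: is the handling of non-starters written down?** It is not. Protocol 6.4 starts treatment at the face-to-face training session in all arms, which suggests that a participant who attended it has received the allocated treatment. Table A8 lists "Missed all training" separately from cross-over, which points the same way. The shared leaflet points the other way. SAP 3.3.2 combines not receiving and not adhering in one deviation category, so it does not settle the question.

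**Step 3: what would follow if non-starters were counted as usual care.** The plan gives no figure for harms to reproduce. The inputs are:

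- Allocation 2:1:1 (Protocol 6.1, SAP 2.2), so 75% of participants are in device arms and 25% in usual care.
- f, the share of each device arm that never starts. The actual rate is not given. 10% is borrowed from the progression criterion as an assumption; 5% and 20% show the range.
- k, the event risk of non-starters relative to starters. This is not in the documents; it is assumed to lie between 0.5 and 2.
- No true effect: every randomised arm has average risk 1.

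Formulas:

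- Starters: s = 1 / ((1 − f) + f·k)
- Usual care as received: U = (0.25 + 0.75·f·k·s) / (0.25 + 0.75·f)
- IMT to usual care ratio: s / U

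At f = 0.10:

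- Share of the usual care group not randomised to it: 0.075 / 0.325 = 23%. With the planned Phase 1 arms of 160, 80 and 80 (160 is stated; the others follow from 2:1:1) this is 24 of 104.
- k = 1.5: s = 1/1.05 = 0.952; U = (0.25 + 0.1071)/0.325 = 1.099; ratio 0.87.
- k = 2: s = 1/1.10 = 0.909; U = (0.25 + 0.1364)/0.325 = 1.189; ratio 0.76.
- k = 0.5: s = 1/0.95 = 1.053; U = (0.25 + 0.0395)/0.325 = 0.891; ratio 1.18.

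| f | k = 0.5 | k = 1 | k = 1.5 | k = 2 |
|---|---|---|---|---|
| 5% | 1.10 | 1.00 | 0.92 | 0.85 |
| 10% | 1.18 | 1.00 | 0.87 | 0.76 |
| 20% | 1.33 | 1.00 | 0.80 | 0.67 |

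These ratios do not depend on trial size. Grouped by allocation, the expected ratio is 1.00 in every cell.

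**The case against.** The strongest reply is that nothing in the documents moves a non-starter into usual care. On the reading supported by Protocol 6.4 and Table A8, someone trained at the first visit who then did no home sessions stays in the device arm, and the distortion in step 3 largely disappears. This stands. A reader might infer from SAP 3.3.3 that non-starters' events will be credited to usual care and that IMT will therefore look safer than it is. The documents support neither half of that inference: the reassignment is not written, and no figure is given for the risk of non-starters.

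The direction is open as well. Frailer patients may be less likely to start. Yet a withdrawal reason named in both documents (Protocol, Discontinuation/withdrawal; SAP 3.4) is a clinical reason for not operating, and a participant without an operation has no postoperative events. That would make non-starters lower risk for Table A13 and reverse the bias.

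Three further points stand. The 10% is a progression threshold across all randomised participants, not an expected rate in the device arms. Harms are only described, with no effect estimate or test planned, in a trial that closed at the end of Phase 1. Table A11 already gives PPC components and mortality by allocation, and Table A8 is repeated by allocation, so non-starters will be visible.

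A separate safety population can also be a deliberate exception to SAP 3.3.1, and the protocol supplies a rationale for grouping by exposure. That rationale covers the training window. It does not reach events from admission onward, and it does not explain the absence of a by-allocation table. Finally, the SAP footer cites protocol version 3.0, whereas the protocol available is version 2.0. A definition of treatment received could be in the later version, but the SAP does not refer to one.

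**Conclusion.** The point holds in a limited form. For adverse and serious adverse events, the only by-arm split specified is by treatment received. That term is undefined, and the split is applied to periods in which the protocol's own exposure rationale no longer operates. The randomised comparison of those events is given up for no stated gain.

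Whether this biases the tables, and which way, cannot be determined from the documents. It depends on how received is interpreted, how many device-arm participants never start, and their risk. Under the least favourable reading, with no true effect and f = 10%, the ratio runs from 1.18 (k = 0.5) through 1.00 (k = 1) to 0.76 (k = 2). These values illustrate sensitivity and do not predict a result.

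The primary outcome, the PPC components and mortality are untouched. The concern is confined to the other adverse events. It is worth correcting because the correction is cheap and removes a choice that would otherwise be made after the data are seen.

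**What to change.** In SAP 3.3.3 and the footnotes to Tables A13 and A14:

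1. Tabulate adverse and serious adverse events from admission onward (index stay, 3 and 6 months) by randomised allocation, in the three arms, as the main by-arm version.
2. Keep the treatment-received split as a supplement, mainly for events in the pre-operative training window.
3. Define received for that supplement, for example as at least one IMT session, and show device-arm participants who did not meet it as their own group, not as usual care.

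The cost is wording and one extra set of tables. No new data are needed, since allocation is already held. The by-allocation version slightly dilutes any exposure-related rate, which the supplement would still show.

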#### 3.4 Withdrawals

Each participant has the right to withdraw at any time for any reason and is not obliged to give their reasons for doing so. Data collected prior to withdrawal will be retained and reported.

A clinician may withdraw a participant at any time if they feel it is in the participant's best interests (e.g., a clinical reason for not performing the surgical procedure is discovered, not possible due to their health).

Reasons for all discontinuations and withdrawals will be captured in the trial database and reported.

The DMSC may recommend cessation of treatment for participants.

## 4. Statistical analyses and report content

#### 4.1 General considerations

The statistical analysis is the responsibility of the BTC study statisticians.

Where interventions are being compared formally using statistical modelling, the usual care and low-resistance IMT groups combined will act as the reference category (see section for 4.4.1 for discussion of initial analysis).

All statistical tests will be superiority comparisons; they will be 2-sided and will be performed using a 5% significance level, with the exception of tests for interactions that will be performed using a 10% significance level.

No formal adjustment will be made for multiple testing, but consideration will be taken in interpretation of results to reflect the number of statistical tests performed and the consistency, magnitude and direction of treatment estimates for different outcomes.

#### 4.2 General calculations

Unless otherwise stated, all percentages will be calculated using the total number of participants from the relevant population as the denominator. For categorical and binary data, all percentages will be rounded to 2 decimal place(s), and for continuous measures, these will be summarised to one more decimal place than the data is collected, etc. P-values >0.001 will be summarised to 2 significant figures, and those <0.001 will be reported as <0.001.

#### 4.3 Outcomes

#### 4.3.1 Primary outcome

The primary outcome will be the incidence of any PPC (a yes/no binary outcome) occurring inhospital (before discharge) or hospital readmission for a PPC within 30 days from surgery in each of the three care groups.

New variable	Rules
Incidence of any PPC	YES: (Any postoperative pulmonary complications in-hospital) OR (Any Hospital
	readmission for postoperative pulmonary

complications within 30 days following surgery)

**NO:** (NO postoperative pulmonary complications in-hospital) AND (NO Hospital readmission for postoperative pulmonary complications within 30 days following surgery)

MISSING: otherwise

**NO:** If participant did not have a mechanical ventilation in hospital post operatively or during a hospital admission within 30 days of

surgery

MISSING: otherwise

Non-invasive ventilation (including continuous positive airway pressure (CPAP) and/or pressure support (BIPAP))

**Atelectasis** 

Pneumothorax

Aspiration pneumonitis

Invasive ventilation

**YES:** If participant did have non-invasive ventilation (NIV) ventilatory support via a facemask/hood post operatively or during a hospital admission within 30 days of surgery

**NO:** If participant did not have non-invasive ventilation (NIV) post operatively or during a hospital admission within 30 days of surgery

MISSING: otherwise

Optiflow (high flow nasal oxygen therapy)

**YES:** If participant did have high flow nasal oxygen (optiflow) in hospital post operatively or during a hospital admission within 30 days of surgery

NO: If participant did not have high flow nasal oxygen (optiflow) in hospital post operatively or during a hospital admission within 30 days of surgery

**MISSING:** otherwise

Length of ICU stay = (ICU discharge date – ICU admission date)

= (Hospital discharge date – surgery date)

YES: If participant was prescribed antibiotic for one or more PPC within 6 months following

surgery

NO: If participant was not prescribed antibiotic for one or more PPC within 6 months following

**MISSING:** otherwise

**YES:** If participant was prescribed bronchodilator within 30 days following

surgery

NO: If participant was not prescribed bronchodilator within 30 days following

surgery

MISSING: otherwise

EQ5D single summary index score Five digit 'state' score is derived as:

> 10000\*mobility score + 1000\*self-care score + 100\*usual activities score + 10\*pain/discomfort

score + anxiety/depression score.

Each state score is then assigned a single summary index score according to reference scales. These index scores are numerical and range from -0.59 to 1.00, with a score of 1.00

denoting perfect health.

Each question is assigned 0 to 3 (4 point

scale). Each question contributes to either Depression score or for the Anxiety score. The total score is calculated as the sum for the

Depression and for the Anxiety.

Scoring of the scale is based on summing the total of all items, each of which is scored from

0-4. For the CD-RISC-10, the full range is

therefore from 0 to 40.

The score for each item is the number circled.

The numbers range from 1 to 10. If two consecutive numbers are circled, the lower number (less self-efficacy) is coded. The score

for the scale is the mean of the six items.

**MISSING:** If more than two items are missing, the scale score is missing.

Length of hospital stay

Antibiotic prescription

Bronchodilator prescription

